Cohort A: The primary endpoint is ORR as assessed by central IRR and analyzed separately for patients with deleterious BRCA1/2 and ATM mutations. ORR for Cohort A is defined as the proportion of patients with a confirmed response of CR or PR using modified RECIST Version 1.1 (ie, CR or PR by IRR assessment and no progression in bone per PCWG3 by IRR assessment).

Cohort B: The primary endpoint is PSA response ($\geq 50\%$ decrease) as assessed by a local laboratory and analyzed separately for patients with deleterious BRCA1/2 and ATM mutations. The proportion of patients with $\geq 50\%$ PSA decrease from baseline will be reported.

Cohort C: The primary endpoint is ORR defined as the proportion of patients with a confirmed response of CR or PR using either modified RECIST Version 1.1 (if measurable visceral and/or nodal disease is present) or $\geq 50\%$ PSA decrease from baseline (if visceral and/or nodal disease is absent). For patients with measurable disease, response will be assessed by central IRR.

Secondary Efficacy Analyses:

Duration of response is defined as the time from the date that a response (modified RECIST Version 1.1 or PSA $\geq 50\%$) is first reported to the time that progression (using modified RECIST Version 1.1/PCWG3 criteria or PSA-progression criteria, respectively) is documented.

Radiologic PFS (rPFS) is defined as the time from first dose of rucaparib to the date of first objective evidence of radiographic progression (soft tissue or bone lesion) or death due to any cause, whichever occurs first. Radiologic disease progression includes confirmed bone disease

progression and soft tissue disease progression adjudicated by independent central radiological review using the PCWG3 guidelines for bone disease and modified RECIST Version 1.1 for soft tissue disease.

OS is defined as the date from first dose of rucaparib to the date of death due to any cause.

CBR is defined as the combination of CR, PR, and SD as defined by modified RECIST Version 1.1 with no progression in bone per PCWG3 criteria. Per RECIST, to be assigned a best overall response of CR or PR, changes in tumor measurements must be confirmed by repeat assessments that should be performed no less than 4 weeks after the criteria for response are first met.

Confirmed PSA response is defined as $\geq 50\%$ reduction in PSA from baseline to lowest post-baseline PSA result, with a consecutive assessment conducted at least 3 weeks later. PSA response will be calculated for all patients with PSA values at baseline and at least 1 post-baseline assessment. PSA will be assessed by a local laboratory.

Time to PSA progression is defined as the time from first dose of rucaparib to the date that a $\geq 25\%$ increase and absolute increase of ≥ 2 ng/mL above the nadir (or baseline value for patients who did not have a decline in PSA) in PSA was measured. The increase must be confirmed by a second consecutive assessment conducted at least 3 weeks later.

Safety Analyses

Adverse events (AEs), clinical laboratory results, vital signs, ECOG performance status, body weight, and concomitant medications/ procedures will be tabulated and summarized. AEs will be summarized overall and separately for SAEs, AESIs, AEs leading to discontinuation, AEs leading to death, and Grade 3 or higher AEs graded using National Cancer Institute Common Terminology Criteria for Adverse Events (CTCAE) Version 4.03 or higher. Body weight and vital signs will be summarized descriptively (N, mean, standard deviation, median, minimum, and maximum). ECOG performance status will be summarized categorically.

A DMC will review safety and efficacy data on a periodic basis to ensure an acceptable overall risk and benefit for patients participating in the study.

Date of Protocol Amendment 4 Approval

24 August 2020

TABLE OF CONTENTS

1	SYNOPSIS.....	4
	LIST OF IN-TEXT TABLES	23
	LIST OF IN-TEXT FIGURES.....	23
2	LIST OF ABBREVIATIONS AND DEFINITIONS OF TERMS.....	24
3	INTRODUCTION	29
3.1	Investigational Product	29
3.2	Background and Rationale for PARP Inhibition	29
3.3	Metastatic Castration-resistant Prostate Cancer.....	29
3.3.1	Treatment of Metastatic Castration-resistant Prostate Cancer.....	30
3.4	Prior Experience with Rucaparib	31
3.4.1	Nonclinical Experience with Rucaparib	31
3.4.2	Clinical Experience with Rucaparib	32
3.5	Rationale for this Study of Rucaparib.....	41
4	STUDY OBJECTIVES.....	44
4.1	Primary Objective	44
4.2	Secondary Objectives.....	44
4.3	Exploratory Objectives	44
5	INVESTIGATIONAL PLAN.....	46
5.1	Overall Study Design and Plan	46
5.1.1	Pre-Screening Phase.....	46
5.1.2	Screening Phase	47
5.1.3	Treatment Phase.....	47
5.1.4	Post-treatment Phase.....	48
5.2	Study Schema.....	49
5.3	End of Study	52
6	STUDY POPULATION SELECTION	53

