- To assess duration of response (DOR)
- To assess radiologic PFS (rPFS)
- To assess overall survival (OS)
- To assess clinical benefit rate (CBR)
- To assess PSA response $\geq 50\%$ (all patients)
- To assess PSA response $\geq 90\%$ (all patients)
- To assess time to PSA progression
- To characterize the steady-state pharmacokinetics (PK) of rucaparib in mCRPC patients
- To assess safety and tolerability

Exploratory Objectives:

- To evaluate Patient-reported Outcome (PRO) using the EuroQol 5 dimensions 5 level questionnaire (EQ-5D-5L), Functional Assessment of Cancer Therapy – Prostate (FACT-P), analgesic drug score, and Brief Pain Inventory – Short Form (BPI-SF) instruments
- To assess changes in the molecular profile over time of matched pre and post-treatment tumor or plasma samples
- To assess concordance in HRR gene mutation status in matched Pre-Screening biopsy tissue, archival primary and metastatic tumor tissue, and plasma circulating tumor DNA (ctDNA)
- To assess ctDNA as a molecular marker of response
- To assess time to first subsequent antineoplastic therapy
- To evaluate loss of heterozygosity (LOH) in metastatic disease site biopsy and archival primary and metastatic tumor tissue samples
- To evaluate mechanisms of response and resistance in ctDNA and progression tumor tissue samples.

Study Design

This is a Phase 2 multicenter study evaluating rucaparib for treatment of patients with mCRPC whose tumors are associated with HRD. This study will enroll mCRPC patients with deleterious mutations in BRCA1/2, ATM, or other HRR genes associated with sensitivity to PARPi ([Appendix 1](#)). All patients will be required to have progressed on prior AR-targeted therapy (abiraterone acetate, enzalutamide, apalutamide, or investigational AR-targeted agent) after receiving treatment with at least 1, but no more than 2, of these agents. Patients must also have progressed after 1 prior line of taxane-based chemotherapy for mCRPC. Patients who received prior PARPi treatment, mitoxantrone, cyclophosphamide or platinum-based chemotherapy will be excluded.

This study consists of a Pre-Screening Phase, Screening Phase, Treatment Phase, and

Post-Treatment Phase. Patients will receive rucaparib monotherapy in the Treatment Phase, and will undergo procedures and assessments including regular safety and efficacy evaluations during the entire conduct of the study.

Pre-Screening Phase

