10. Non-study related minor surgical procedure within < 5 days, or major surgical procedure within < 21 days, prior to first dose of rucaparib; in all cases, the patient must be sufficiently recovered and stable before treatment administration
11. Presence of any other condition that may increase the risk associated with study participation or may interfere with the interpretation of study results, and, in the opinion of the investigator, would make the patient inappropriate for entry into the study

Study Treatment

The starting dose and schedule of rucaparib is 600 mg ingested twice a day (BID). Patients may take rucaparib with or without food. Each dose should be taken with at least 8 oz (240 mL) of water as close to 12 hours apart as possible, preferably at the same times every day. Rucaparib will be provided as 200, 250, and 300 mg dose strength tablets. Tablets should be swallowed whole.

Dose holds or reductions are permitted in the event of unacceptable toxicity.

Patients will receive rucaparib until confirmed radiologic disease progression as assessed by investigator using modified RECIST Version 1.1 and/or PCWG3 (for bone lesions only) criteria, unequivocal clinical disease progression, unacceptable toxicity or inability to tolerate further treatment, loss to follow-up, or withdrawal of consent. However, if a patient receiving rucaparib has met criteria for confirmed radiologic disease progression by modified RECIST Version 1.1 and/or PCWG3 criteria, but the patient continues to derive clinical benefit per the investigator, then continuation of treatment will be permitted with additional consent.

Concomitant Medications

During the study, supportive care (eg, antiemetics; analgesics for pain control) may be used at the investigator's discretion and in accordance with institutional procedures. Supportive care must be recorded for each patient in the appropriate section of the eCRF.

Erythropoietin, darbepoetin alfa, and/or hematopoietic colony-stimulating factors for treatment of cytopenias should be administered per standard of care and according to institutional guidelines. Transfusion thresholds for blood product support will be in accordance with institutional guidelines.

Palliative radiotherapy for the treatment of painful bony metastasis is permitted during the study. Treatment with rucaparib should be held prior to initiation of radiation therapy and until the patient has recovered from any radiation-related toxicity.

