8.1 Supportive Care

During the study, supportive care (eg, antiemetics; analgesics for pain control) may be used at the investigator's discretion and in accordance with institutional procedures. Supportive care must be recorded for each patient in the appropriate section of the eCRF.

Continuation of low-dose corticosteroid therapy that has been stable prior to study entry is permitted (see [Section 6.3](#)). A low dose is considered 5-15 mg/day of prednisone or prednisolone, and 0.5-3 mg/day of dexamethasone.

Erythropoietin, darbepoetin alfa, and/or hematopoietic colony-stimulating factors for treatment of cytopenias should be administered per standard of care and according to institutional guidelines. Transfusion thresholds for blood product support will be in accordance with institutional guidelines.

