9 STUDY PROCEDURES AND ACTIVITIES BY VISIT

9.1 Schedule of Assessments

[Table 5](#) summarizes the procedures and assessments to be performed for all patients. Study procedures and assessments should be performed as close to the scheduled time as possible, but within ± 3 days of the scheduled time unless otherwise stated.

Table 5. Schedule of Assessments

Procedure ^a	Pre-screening Phase	Screening Phase		Treatment Phase					Post-Treatment Phase		
				Week 1	Week 3	Week 5	Week 7	Week 9 & every 4 weeks thereafter			
		Day -28 to Day -1	Day -14 to Day -1	Study Day 1 ^b	Study Day 15	Study Day 29	Study Day 43	Day 57 & every 28 days thereafter	Treatment Discontinuation	28-day Follow-up	Long-term Follow-up
Informed Consent	X ^c	X									
BRCA, ATM or other HRR gene mutation assessment from ctDNA blood and tumor sample ^{c, d}	X ^c										
Medical/Oncology History ^e		X									
Blood samples for plasma ctDNA analysis ^f		X		X		X		X	X		
Physical Examination, Weight, Height ^g		X		X	X	X	X	X	X	X	
Vital Signs ^h		X		X	X	X	X	X	X	X	
12-lead ECG ⁱ		X							X		
Prior/Concomitant Medications/Procedures		X		X	X	X	X	X	X	X	
Tumor Assessment/CT/MRI and Bone Scan ^j		X		End of every 8 weeks from Study Day 1, up to 24 weeks (Study Weeks 9, 17, 25) and then every 12 weeks thereafter (Study weeks 37, 49, 61, etc.) ^k					X ^l	X ^l	X ^l
Archival Primary/ Metastatic Tumor Tissue Sample for retrospective testing ^m		X									
Patient-reported outcome (BPI-SF, analgesic drug score, FACT-P, EQ-5D-5L) ⁿ			X	X		X		X	X	X	X
ECOG Performance Status			X	X	X	X	X	X	X	X	
Serum Testosterone		X									
PSA Measurement ^o		X		X		X		X	X		
Clinical Laboratory Assessments ^p			X	X	X	X	X	X	X	X	
Pharmacogenomic blood sample ^q				X							
Study Drug Dispensation				X		X		X			
Adverse Events ^r	(X)	(X)	(X)	X	X	X	X	X	X ^s	X ^s	
Plasma PK Sample						X ^t		X ^t			

Post-progression Tumor Biopsy (Optional)										X ^u		
Subsequent Treatments, AESIs, & Survival ^v											X	X

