9.14 Patient Reported Outcomes (Health and Quality of Life Questionnaires)

Patient reported outcomes utilizing the BPI-SF, ([Appendix 6](#)), FACT-P ([Appendix 7](#)), EQ-5D-5L ([Appendix 8](#)), and analgesic drug score instruments ([Appendix 9](#)) will be assessed during screening, Study Day 1 and every 28 days thereafter, at the Treatment Discontinuation Visit, at the 28-Day Follow-up Visit, and if applicable, during long term follow-up. The analgesic drug score will be recorded according to the WHO's analgesic ladder: 0 for no analgesic, 1 for nonopioids, 2 for opioids for moderate pain, and 3 for opioids for severe pain.⁴⁶

Patients should complete the instruments before any other scheduled study procedures are performed and dosing occurs (if applicable). For patients who discontinued treatment prior to radiologic disease progression, PRO assessments should be collected until subsequent radiologic disease progression was documented.

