Appendix 9 Analgesic Use Questionnaire

A sample form for the Analgesic Use Questionnaire is included on the next page.

Study ID #	CO-338-052 (TRITON2)	Site No	
Patient ID:	52- _____ - _____	Date	

Analgesic Use Questionnaire

Please indicate the strongest pain medication you have taken within the past 24 hours:

- 0 = No pain medication
- 1 = Non-opioid pain medication such as aspirin [salicylate], acetaminophen [paracetamol], other non-steroidal anti-inflammatory drug [NSAID], etc.
- 2 = Mild opioid pain medication such as codeine, hydrocodone, tramadol, etc.
- 3 = Strong opioid pain medication such as morphine, oxycodone, hydromorphone, fentanyl, methadone, etc.

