10.3 Exploratory Efficacy Analyses

10.3.1 Patient-reported Outcome

Patient reported outcome endpoints by FACT-P and BPI-SF will be summarized according to their respective scoring manuals.

Analgesic drug score will be recorded according to the World Health Organization (WHO) scale (0 for no medication, 1 for non-opioid pain medication, 2 for opioids for moderate pain, and 3 for opioids for severe pain).

Analyses of change and/or percent change from baseline will be analyzed for each scheduled post-baseline visit and for the final visit for the EQ-5D-5L VAS.

Patients who do not have both a baseline measurement and at least one post-baseline measurement will not be included.

PRO endpoints will be summarized for all patients and may also be summarized for the subgroups of patients defined by measurable disease status at baseline.

BPI-SF

The primary analysis of change in pain intensity over time will be assessed using BPI-SF Item #3 (pain symptoms at their worst over the last 24 hours). A composite assessment of change in pain intensity (Item #3-6, worst pain, least pain, average pain, and current pain, respectively) will also be analyzed.

BPI item scores, change from baseline, and percentage change from baseline in daily pain intensity will be summarized at each visit and at the final visit using descriptive statistics (N, mean, SD, minimum, median, and maximum).

Longitudinal plots of the mean changes from baseline to each scheduled visit may also be presented. These plots may exclude visits for which only a small percentage (e.g., $\leq 30\%$) of patients have data.

FACT-P

Scores and post-baseline score changes for the FACT-P global, physical, functional, and prostate-cancer scale scores as well as scores for the FACT-P trial outcome index (TOI) will be summarized at each visit and at the final visit using descriptive statistics (N, mean, SD, minimum, median, and maximum).

Longitudinal plots of the mean changes from baseline to each scheduled visit may also be presented. These plots may exclude visits for which only a small percentage (e.g., $\leq 30\%$) of patients have data.

EQ-5D-5L

Change and percent change from baseline will be analyzed at each visit and at the final visit for EQ-5D-5L VAS. Patients who do not have both a baseline measurement and at least one post-baseline measurement will not be included.

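### Change in BPI-SF worst pain is analysed without the analgesic score collected at the same visits, so a change in pain cannot be told apart from a change in analgesia

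*Protocol*

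**What the plan says.** The protocol's exploratory objectives (Synopsis and section 4.3) list the patient-reported instruments in one item, including "FACT-P), analgesic drug score, and Brief Pain Inventory". The schedule of assessments (section 9.1, Table 5) puts them in a single row: "Patient-reported outcome (BPI-SF, analgesic drug score, FACT-P, EQ-5D-5L". Section 9.14 says they "will be assessed during screening, Study Day 1 and every 28 days thereafter", then at treatment discontinuation, at the 28-day follow-up and, where applicable, in long-term follow-up.

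The analgesic form (Appendix 9) reads "Please indicate the strongest pain medication you have taken within the past 24 hours" and is scored 0 to 3. BPI-SF Item 3 (Appendix 6) asks for worst pain over the last 24 hours on a 0-10 scale.

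On analysis, SAP section 10.3.1 says "The primary analysis of change in pain intensity over time will be assessed using BPI-SF Item #3", with a composite of Items 3 to 6 as a further analysis. Scores, change and percentage change are summarised descriptively at each visit and at the final visit. For the other instrument it says "Analgesic drug score will be recorded according to the World Health Organization (WHO) scale". SAP Table 1 and protocol section 11.5.3.1 say no more than that.

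On analgesic use, protocol section 8.1 says "supportive care (eg, antiemetics; analgesics for pain control) may be used at the investigator's discretion". Section 8.2 also permits palliative radiotherapy for painful bone metastases. Section 7.5 confirms that every enrolled patient receives open-label rucaparib.

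**The concern.** Reported pain reflects both the disease and the pain relief being given. If Item 3 falls at the visit where the patient first reports a strong opioid, the fall may owe nothing to rucaparib. If Item 3 is flat while the patient has come off opioids, real benefit may be missed. In a randomised trial a control arm would share some of this; here there is none.

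The exposure is greatest late in follow-up. Pain scores continue through treatment discontinuation and, for patients who stop before radiographic progression, until progression is confirmed. Patients treated beyond progression keep having the protocol assessments other than scheduled imaging (protocol section 7.4.4). Analgesic needs are plausibly changing most at those times.

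What is at stake is how the pain results are read. A mean fall in Item 3 would invite the statement that pain improved on rucaparib. The variable needed to qualify that statement is already collected, but the plan gives it no role in the pain analysis.

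**Working it through.** The plan states no sample size, power, alpha or effect size for BPI-SF or the analgesic score, so there is no figure to reproduce. The check is of the text, followed by one illustration.

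**1. Can the two measures be paired?** Yes. They share the same visits (Table 5, section 9.14), and Item 3 and the analgesic score share the 24-hour window (Appendices 6 and 9).

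**2. Does the plan pair them?** No. SAP section 10.3.1 gives descriptive statistics of Item 3 and of the composite, with no analgesic term, stratum or rule. It does not say that the summary is meant to apply regardless of analgesic use. SAP section 13, which lists changes from the protocol, does not mention it.

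**3. Will the score be shown at all?** Probably. SAP section 9.3 lists it as a patient-reported variable, section 10.3.1 says such endpoints will be summarised for all patients, and section 3 presents categorical variables as frequencies and percentages. That gives a table of the score by visit. It does not show whether the patients whose pain fell are those whose score rose.

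**4. What does the Item 3 summary do with each pattern?**

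| Item 3 change | Analgesic score change | Enters the mean as | Could reflect |
|---|---|---|---|
| Fall | None or down | Fall | Improvement |
| Fall | Up | Fall | Added analgesia, benefit, or both |
| None | Down | No change | Improvement hidden by less analgesia |
| None | Up | No change | Worsening masked by more analgesia |
| Rise | Any | Rise | Worsening, or less analgesia |

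Rows 1 and 2 cannot be told apart in the planned output, and neither can rows 3 and 4.

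**5. Illustration, on assumptions that are not in the documents.** Suppose rucaparib has no effect on pain, 10% to 40% of patients step up a class, and the step-up lowers Item 3 by 1 to 3 points in them.

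Shift in mean change = -(share stepping up) x (points relieved)

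- Low end: -(0.10 x 1) = -0.1 points.
- High end: -(0.40 x 3) = -1.2 points.

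The same shares and points applied to step-down give +0.1 to +1.2 points, and equal amounts of each cancel. The assumed inputs set both the size and the sign of the result.

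**The case against.** The strongest reply is that this is an exploratory, descriptive endpoint with no hypothesis, alpha or decision rule. Mean pain change regardless of analgesic use is a legitimate summary, and the plan does not claim that it isolates a rucaparib effect. Concomitant treatments are tabulated anyway (SAP section 7), and the BPI-SF form itself asks about pain treatment and relief. All of this is true, and it is why the point is minor. But these are separate tabulations, and none connects pain change to analgesic change in the same patient.

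A reader might infer three stronger things, which the documents do not support:

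- **That the analgesic score is never summarised.** SAP sections 9.3 and 10.3.1 together imply a separate summary. What is missing is the link to pain.
- **That a patient who steps up to a strong opioid is counted as improved.** SAP section 10.3.1 has no responder or improvement category; such a patient simply contributes a negative change to the mean.
- **That the bias always favours rucaparib.** Patients can also step down, which works the other way. A step-up that follows a rise in pain may only bring the score back towards baseline.

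It is also fair to say that a joint analysis does not isolate a drug effect. The score records the strongest class taken, not the dose, so an increase within a class is invisible and a patient already at 3 cannot register a rise. Palliative radiotherapy is not captured. Groups defined by analgesic change after baseline are partly outcomes of disease and treatment. These limits stand and should be stated with the results; they do not remove the value of showing the two measures together.

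**Conclusion.** The point holds as a minor one. SAP section 10.3.1, like protocol section 11.5.3.1, gives the analgesic score no role in the analysis of BPI-SF pain, although the two are collected together and Item 3 covers the same 24 hours. In a single-arm study this leaves a change in pain indistinguishable from a change in analgesia, in either direction.

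The size cannot be derived from the documents, which give neither the frequency of analgesic changes nor their effect on Item 3. The illustrative 0.1 to 1.2 points either way rests wholly on assumed inputs and should not be cited as an estimate. No primary endpoint, secondary endpoint or interim decision uses these data.

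**What to change.** Amend SAP section 10.3.1 as follows.

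1. Keep the planned Item 3 summary and label it as describing pain regardless of analgesic use.
2. Add a supportive joint description, by visit and at the final visit, relative to baseline:
   - improvement: Item 3 falls and the analgesic score does not rise;
   - worsening: Item 3 rises or the analgesic score rises;
   - step-down at stable pain: Item 3 unchanged and the score lower, shown as its own category;
   - unchanged: neither moves.

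   These cover all nine combinations of fall, no change or rise in Item 3 with down, same or up in the score (2 + 5 + 1 + 1 = 9), without overlap. The SAP should state in advance what size of Item 3 change counts as a fall or a rise; the documents give no threshold.
3. Add a baseline-to-visit shift table of the analgesic score, cross-tabulated with Item 3 change.
4. State the limits: the score captures class, not dose; palliative radiotherapy is not covered; and groups defined by post-baseline analgesic change are descriptive only.

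The cost is SAP wording and a few tables from data already collected, with no new visits and no change in care. The drawback is smaller groups per visit, most noticeable late in follow-up.
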